8.0 EVALUATION AND END POINTS

The approximate timing for administration of the assessments for this study is detailed in **Table 1** and **Figure 3**. Administration of all assessments will be event-driven but will approximately correspond to the time points illustrated in **Table 1** and **Figure 3**. These time points are recommended dates that could be completed within a limit of 30 days from the proposed time points to take into account suitability of patients’ clinical status and reasonable recovery of peripheral blood counts.

Patients who are offered and then treated with HCT will have assessments done at approximately 3, 6, 12, and 18 months after day 0 of HCT. For patients treated with non-HCT treatments (additional conventional therapy or follow up/supportive care), assessments will be done at time points that are roughly corresponding to those who received transplants, which will be at approximately 9, 12, 18, and 24 months from study enrollment. Patients who haven’t received further treatment after 6 months from date of study enrollment should follow the time points for assessments for non-HCT treatments. Should these patients later be treated with allogeneic HCT, then dates of assessments will be readjusted to reflect those designed for recipients of HCT (3, 6, 12, and 18 months after day 0 of HCT).

Protocol 2368.00

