Physical activity as a component of the Fried Frailty Index is measured by a subscale of the Medical Outcomes Study (MOS) Physical Health. The MOS Physical Health Scale measures a broad range of physical functioning, with questions ranging from “Can you bathe and dress yourself?” to “Can you perform vigorous activities, such as running or lifting heavy objects?” Items are rated on a 3-point Likert scale measuring independence in performing the activity. Internal consistency of the physical function score is 0.92.[99]

QOL measures will be assessed at:

- 1) Study enrollment.
- 2) After approximately 1 months from study enrollment and at least 28 days from last therapy cycle.
- 3) After approximately 3 months from study enrollment and at least 28 days from last therapy cycle.
- 4) After approximately 6 months from study enrollment and, if necessary, adjusted within a limit of 30 days to have this assessment done prior to treatment with either allogeneic HCT or additional non-transplant therapies.
- 5) At 3, 6, 12, and 18 months after day 0 of allogeneic HCT for recipients of HTC or at 9, 12, 18, and 24 months from study enrollment for patient not treated with HCT.

8.1.15 OARS Multidimensional Functional Assessment Questionnaire (OMFAQ):

Each patient will complete an assessment of his/her respective functional status as a measurement of ability to perform activities of daily living. A portion of the OARS Multidimensional functional Assessment Questionnaire (OMFAQ) will be administered, as it gives a view of the patient’s functional status and independence, including: social, economic, mental and physical health, and self-care capacity. The first part includes seven questions regarding the instrumental activities of daily living (commuting, cooking, shopping, and ability to handle finances). The second part includes seven questions regarding the activities of daily living (bathing, dressing, toileting, walking). The scores range from 0 to 2, with lower scores indicating higher levels of dependency on others to complete the activities. The assessment is estimated to take 5 minutes. The OMFAQ will be scored according to the recommendations of the developers. The measures have good validity [100].

These variables will be assessed at:

- 1) Study enrollment.
- 2) After approximately 1 months from study enrollment and at least 28 days from last therapy cycle.
- 3) After approximately 3 months from study enrollment and at least 28 days from last therapy cycle.

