¥If a patient received an allogeneic HCT, then study assessments will be adjusted to reflect the durations of pre-transplant and 3, 6, 12, and 18 months after day 0 of HCT.

Protocol 2368.00

Figure 3: Prospective observational study schema

Protocol 2368.00

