(3) Secondary Outcomes: **(i)** The relationship between the choice of treatment (HCT vs. non-HCT) and QOL, function, utilization, and satisfaction scores will be examined. Intra-patient differences will be used to analyze changes in QOL from baseline to follow-up assessments. Basic analyses will utilize paired t-tests (for changes over time) and two-sample t-tests (for comparison between groups). In order to make full use of the longitudinal data we will also use generalized estimating equations (GEEs) approach,[118] which can accommodate the within patient correlation structure and arbitrary patterns of missing data. Further, the GEEs approach would allow for the population-average interpretation which is an advantage over, for example, generalized linear mixed models approach.

(ii) The previously described statistical approaches will be used to adjust the comparisons between recipients of allogeneic HCT and conventional therapy for the pre-exposure measures of QOL and preference scores.

(iii) We will compare the quality-adjusted outcomes using the Q-TWiST methodology which weights survival time according to clinical status (alive without relapse or toxicity, relapse, and toxicity) [119-122]

(4) Tertiary Outcomes: **(i)** The risk factors for mortality after ICU admission in patients with AML will be examined. Survival analysis with logistic regression or Cox proportional hazards model will be used, depending on completeness of patient follow-up. Variables in the model will include the AML-comorbidity model score, history of HCT, AML disease status, absolute neutrophil count, use of life support devices, bacteremia, and creatinine. The above risk factors will be evaluated using AUC and c-statistic to inform development of a potential model to predict ICU mortality. **(ii)** The outcomes of patients with secondary AML will be evaluated as compared to patients with primary AML, after adjusting for percent blasts in the peripheral blood, white blood cell count, and performance status at time of presentation.

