11.4 Missing Data

Protocol 2368.00

This specific aim depends on a high response rate from patients in providing data. The PI together with the SCCA data coordinator will monitor compliance with the self-reported data on a monthly basis and institute corrective measures if the response rate falls below 75%. These may include closer tracking of patients to make sure clinically significant time points are recognized and evaluation of factors associated with no-response in order to identify populations which require greater efforts. Upon receipt of patient-reported data, completion of individual items will be assessed immediately, so that missing data can be requested.

The linear mixed models analysis will be able to accommodate arbitrary patterns of missing data; however, graphical presentations and logistic regression analysis will be performed to understand the missing data mechanism as well as to identify factors associated with incomplete data for survivors. Plots of change in QOL scores from baseline to 90 days, 6 months, 1-year, and 2-year stratified by time of drop-out will be generated separately for each group to determine pattern of missing data. Logistic regression will be used to identify baseline and clinical characteristics associated with missing data. All demographics and baseline characteristics will be included in the logistic model.

Protocol 2368.00

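### The QOL group comparison has no stated time axis, although recipient and non-recipient visits line up only if HCT falls about 6 months after enrolment

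*Combined protocol and SAP*

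**What the plan says.** Section 8.0 gives recipients "assessments done at approximately 3, 6, 12, and 18 months after day 0 of HCT". Patients on other treatment are seen at times "which will be at approximately 9, 12, 18, and 24 months from study enrollment", and the stated intention is that "assessments will be done at time points that are roughly corresponding to those who received transplants". Section 8.1.14 applies both clocks to the QOL measures, the second of them counted from enrolment: "At 3, 6, 12, and 18 months after day 0 of allogeneic HCT for recipients of HTC or at 9, 12, 18, and 24". Table 1 has one set of columns, and its footnote moves recipients to the other clock: "study assessments will be adjusted to reflect the durations of pre-transplant and 3, 6, 12, and 18 months after day 0 of HCT".

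The time of HCT is left open. Patients with no further treatment by month 6 follow the non-HCT schedule, and "Should these patients later be treated with allogeneic HCT, then dates of assessments will be readjusted". Section 11.3 (2)(i) says HCT may come well after consolidation and makes it a time-dependent covariate for NRM, OS and DFS, so that the patients compared have survived equally long. Section 11.3 (2)(ii) adds landmarks at 3, 6 and 9 months, split by prior HCT.

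QOL is a primary objective (5.1.2.2) but is analysed under secondary outcomes in 11.3 (3). That section uses within-patient change from baseline, paired t-tests over time, "two-sample t-tests (for comparison between groups"), and GEE. Item (ii) extends the earlier approaches to adjust for QOL and preference scores measured before exposure.

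**The concern.** A QOL score at a visit depends on treatment and also on how long ago induction was given and on the patient having lived to that visit. If the two groups sit at different points on that course, a difference in mean change is not an HCT effect.

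The plan deals with this for the time-to-event outcomes. It writes no equivalent for QOL: 11.3 (3) gives no time origin, no rule for which visits are set against each other, and no rule for assigning a patient's non-HCT visits when HCT comes later. At stake is the interpretation of a primary objective that the protocol says is needed for decision-making in older patients.

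**Working it through.** **Inputs.** Recipient visits at h = 3, 6, 12, 18 months after day 0, and non-recipient visits at 9, 12, 18, 24 months from enrolment (8.0, 8.1.14). Visit tolerance 30 days (8.0). Expected groups of 170 and 505 (11.1). The documents give no distribution of enrolment-to-HCT time T, and no QOL slope or SD.

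**Step 1: reproduce the plan's correspondence.** 9 - 3 = 12 - 6 = 18 - 12 = 24 - 18 = 6. The two schedules match exactly for HCT at month 6.

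**Step 2: offset for other HCT times.** A recipient's visit falls at T + h from enrolment and its counterpart at h + 6. Offset = (T + h) - (h + 6) = T - 6, the same at all four pairs.

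| HCT month T | Recipient visits, months from enrolment | Offset (months) |
|---|---|---|
| 3 | 6, 9, 15, 21 | -3 |
| 5 | 8, 11, 17, 23 | -1 |
| 6 | 9, 12, 18, 24 | 0 |
| 7 | 10, 13, 19, 25 | +1 |
| 9 | 12, 15, 21, 27 | +3 |
| 12 | 15, 18, 24, 30 | +6 |

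The 30-day tolerance is about as large as the offset for T = 5 to 7. It does not cover the offset at T = 3, 9 or 12.

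**Step 3: survival condition.** A recipient's first post-HCT visit needs survival to T + 3, and its counterpart needs survival to month 9. These agree only at T = 6. Membership of the HCT group also requires survival to T.

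**Step 4: bias in the group mean.** If QOL changes linearly at b per month for reasons unrelated to HCT, setting corresponding visits against each other gives a bias of b × (mean T - 6), with the mean taken over recipients contributing at that visit. Early and late transplants offset each other, and the bias is zero if mean T = 6. With curvature c (a term c × time²), a mean of 6 still leaves c × Var(T). For example, half transplanted at month 3 and half at month 9 gives Var(T) = 9 and a bias of 9c.

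**Step 5: illustration on assumed values.** Take no true group effect, a QOL drift of 0.01 to 0.05 SD per month and a net offset of 3 months. The spurious difference is 0.03 to 0.15 SD. With 170 and 505 patients, the SE is √(1/170 + 1/505) = 0.0887 SD, and a two-sided 5% test rejects 6.3% to 39.4% of the time. With half of each group contributing, it rejects 5.7% to 22.3%. With zero net offset it stays at 5%. The drift and the offset are assumptions; the documents support neither value.

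**The case against.** The strongest reply is that the 6-month shift is deliberate, the text claims only rough correspondence, and event-driven visits are a declared design choice. For HCT at months 5 to 7 the mismatch is no more than a month. This stands: the offset is conditional on HCT timing, and the schedule itself needs no change.

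Second, the t-tests are labelled basic, GEE is also planned, and item (ii) carries the earlier methods over. This stands in part. GEE allows for within-patient correlation but does not supply a time axis or a treatment state. Item (ii) names adjustment for pre-exposure scores and does not say how time-dependent HCT applies to a score at a visit. Section 11.3 (1) promises a comparison of survivors at 3, 6 and 9 months, but for two unnamed outcomes after listing eight, so whether QOL is covered is unclear.

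A reader might infer several stronger points that the documents do not support:
- That the groups are in fact compared months apart. This depends on when HCT occurs, which is not given.
- That the t-tests are run at matched visit labels, or that visits before a late HCT are credited to HCT. The plan states neither; the gap is that it gives no rule.
- That only HCT near month 6 yields a recipient visit at month 24. HCT at month 12 also does (12 + 12 = 24).
- That the plots in 11.4 ("Plots of change in QOL scores from baseline to 90 days, 6 months, 1-year, and 2-year") show the same fault. They are stratified by drop-out time and drawn separately by group to study missingness, and are not group comparisons.

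**Conclusion.** The concern holds in conditional form and is worth correcting before the QOL analysis is run. Corresponding visits align only for HCT at about month 6 and otherwise differ by T - 6 months. The plan expects T to vary, and the QOL comparison as written has no time axis and no rule for visits before a late HCT. The estimated difference can therefore combine the HCT effect with time since enrolment and survival to HCT.

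The size cannot be fixed from the documents. Multiplying the largest individual offsets by a guessed slope would not measure it, because what matters under a linear trend is the mean HCT month. The bias could be nil or material. The rejection rates above show how it would behave under assumed inputs and are not a forecast.

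**What to change.** Keep the visit schedule and amend 11.3 (3):
- Make the longitudinal model (GEE) the primary QOL group comparison, on actual time since enrolment.
- Enter HCT as a time-varying state, so that visits before HCT count as non-HCT, and enter time since HCT as a separate term.
- Make the two-sample t-tests descriptive only.
- Report the distribution of enrolment-to-HCT time, so that readers can judge the offset.

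This extends to QOL the logic that 11.3 (2)(i) already applies to survival outcomes. A landmark comparison would be a reasonable supporting analysis.

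The cost is a little more analysis work, with nothing new for patients or sites in the visit schedule. One practical condition is that the time variable must be the date the survey was completed. Section 9.0 has paper surveys entered by a coordinator after receipt, so the REDCap entry stamp can be later than completion. The documents do not say that a completion date is captured for every survey; this should be confirmed.

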8.1 ASSESSMENTS

8.1.1 Patient-reported socio-demographic variables

- 8.1.1.1 Race and ethnicity.
- 8.1.1.2 Age.
- 8.1.1.3 Gender.
- 8.1.1.4 Marital status and living situation.
- 8.1.1.5 Religiosity/spirituality.
- 8.1.1.6 Work status.
- 8.1.1.7 Income.
- 8.1.1.8 Insurance status.
- 8.1.1.9 Tobacco, alcohol, and recent food intake history.
- 8.1.1.10 Parenthood.
- 8.1.1.11 Educational level as classified into five categories: some high school or less, high school graduate, vocational college or some college, college degree, or professional degree [52,77]. Education is especially important in our study since the majority of subjects are outside the labor market.
- 8.1.1.12 Zip-code of the primary residence. Each zip-code data point will be geocoded using the ArcGIS 9.3 Street-Map North America Postal U.S. address locator (ESRI, Redlands, CA). The location of the treating center will be geocoded into a separate map layer using the U.S. Streets address locator. The ArcGIS Network Analyst extension (ESRI) will be used to calculate driving distance and average driving time along the street network between zip-code of primary residence to the treating center for each patient.

These variables will be assessed once at:

- 1) Study enrollment.

8.1.2 AML or MDS diagnostic features

- 8.1.2.1 In peripheral blood and/or bone marrow, information on:
 - 8.1.2.1.1 Morphological diagnosis (See study documents '2008 WHO Classification of AML and 2008 WHO Classification and Criteria for MDS').
 - 8.1.2.1.2 Flow cytometry.
 - 8.1.2.1.3 Cytogenetics and molecular abnormalities:
 - 8.1.2.1.3.1 AML risk-classification (See study document 'AML Risk Status Based on Cytogenetics and Molecular Abnormalities').
 - 8.1.2.1.3.2 MDS features (See study document 'International Prognostic Scoring System for MDS').
 - 8.1.2.1.4 International prognostic scoring system-Revised (IPSS-R) for patients with MDS (See study document 'International Prognostic Scoring System for MDS').
- 8.1.2.2 In case of extra-medullary disease:
 - 8.1.2.2.1 Flow cytometry of cerebro-spinal fluid.
 - 8.1.2.2.2 Physical examination assessment of any soft tissue mass (chloroma).

Protocol 2368.00

8.1.2.2.3 Imaging descriptions of any soft tissue mass (chloroma).

These variables will be assessed once at:

- 1) Study enrollment.

8.1.3 PFT, Blood Tests, and Urine Analysis (for patients of FHCRC only)

8.1.3.1 Pulmonary function tests: particularly, diffusion capacity of carbon monoxide (DLco) after correction for hemoglobin and forced expiratory volume in one second (FEV1).

8.1.3.2 Serum ferritin, albumin, C-reactive protein (CRP), and vitamin D.

8.1.3.3 Urine test: Albumin-creatinine ratio, as well as urine analysis.

These variables will be assessed once at:

- 1) Study enrollment.

8.1.4 HCT-CI, comorbidities, and laboratory tests:

8.1.4.1 Left ventricular ejection fraction, if available or clinically indicated. The closest value (include the date) to the study assessment point. Liver function tests: particularly, total and direct bilirubin, aspartate aminotransferase, alanine aminotransferase, and albumin. The closest values (include the dates) to the study assessment point.

8.1.4.2 Weight and height and calculation of body mass index. The closest measurements (include the dates) to the study assessment point

8.1.4.3 Laboratory tests, if available or clinically indicated: The closest values (include the dates) to the study assessment point:

8.1.4.3.1 Absolute neutrophil count.

8.1.4.3.2 Hematocrit percentage.

8.1.4.3.3 Platelet count.

8.1.4.3.4 Serum creatinine.

8.1.4.3.5 Lactate dehydrogenase.

8.1.4.3.6 Serum ferritin.

8.1.4.3.7 Beta-2 microglobulin.

8.1.4.4 HCT-CI total score and positive comorbidity findings (Please see study documents for HCT-CI and the comorbidity coding tool). If some of the comorbidities included in the HCT-CI were not assessed for a patient, then indicate not available or "NA".

8.1.4.5 Other positive comorbidities, which are not included in the HCT-CI.

These variables will be assessed at:

- 1) Study enrollment.
- 2) After approximately 3 months from study enrollment and at least 28 days from last therapy cycle.
- 3) After approximately 6 months from study enrollment and, if necessary, adjusted within a limit of 30 days to have this assessment done prior to treatment with either allogeneic HCT or additional non-transplant therapies.

8.1.5 Karnofsky performance status (KPS) percentage:

Protocol 2368.00

Please see study document 'The Karnofsky Performance Status Scale' for KPS assessment.

- 8.1.5.1 As prospectively assessed and documented by clinicians.
- 8.1.5.2 If not assessed by clinicians at the required study time points: there two options.
- 8.1.5.3 Request KPS assessment from treating physician.
- 8.1.5.4 Assignment of KPS by study coordinators at their respective sites after review of medical records.
- 8.1.5.5 Source of KPS assessment should be noted (clinician versus study coordinator)

KPS will be assessed at:

- 1) Study enrollment.
- 2) After approximately 3 months from study enrollment and at least 28 days from last therapy cycle.
- 3) After approximately 6 months from study enrollment and, if necessary, adjusted within a limit of 30 days to have this assessment done prior to treatment with either allogeneic HCT or additional non-transplant therapies.
- 4) At 9, 12, 18, and 24 months from study enrollment for patient not treated with HCT or at 3, 6, 12, and 18 months after day 0 of allogeneic HCT for recipients of HTC.

8.1.6 **Patient preference surveys:**

- 8.1.6.1 Patient-reported survey (See study document 'Patient Preference survey) will collect information on:
 - 8.1.6.1.1 Patients' preferred level of involvement in treatment decision-making [53].
 - 8.1.6.1.2 Patients' values regarding length of life vs. QOL.
 - 8.1.6.1.3 Patients' perceptions of the risks and benefits of allogeneic HCT versus other therapies.
 - 8.1.6.1.4 Patients' confidence in their knowledge about allogeneic HCT versus other therapies.
 - 8.1.6.1.5 Patients' estimates of their chances of cure and survival at 1-year.

These variables will be assessed at:

- 1) Study enrollment.
- 2) After approximately 1 month from study enrollment and at least 28 days from last therapy cycle.
- 3) After approximately 3 months from study enrollment and at least 28 days from last therapy cycle.
- 4) After approximately 6 months from study enrollment if the patient has not undergone HCT.

8.1.7 **Physician-reported surveys:**

- 8.1.7.1 8.1.7.1 Physician-reported survey (See study documents 'MD Demographics survey and MD Survey') will collect information on:
 - 8.1.7.1.1 Physicians' characteristics.

Protocol 2368.00

- 8.1.7.1.2 Physicians' assessment of their respective patients' preferences for involvement in treatment decision making using Degner's validated tool [53].
- 8.1.7.1.3 Physicians' estimates of their respective patients' chances of cure and survival at 1-year.

These variables will be assessed at:

- 1) Study enrollment.
- 2) After approximately 1 month from study enrollment and at least 28 days from last therapy cycle.
- 3) After approximately 3 months from study enrollment and at least 28 days from last therapy cycle.
- 4) After approximately 6 months from study enrollment if the patient has not undergone HCT.

8.1.8 Availability of donor:

We will collect information on:

- 8.1.8.1 Whether the patient has a potentially available donor.
- 8.1.8.2 Whether the patient has a definitely available donor.
- 8.1.8.3 Type of donor: related, unrelated, or cord blood.
- 8.1.8.4 Degree of HLA-matching: matched, single allele mismatch, one antigen mismatch, HLA-haploidentical, or others.

These variables will be assessed at:

- 1) Study enrollment.
- 2) After approximately 1 month from study enrollment and at least 28 days from last therapy cycle.
- 3) After approximately 6 months from study enrollment and, if necessary, adjusted within a limit of 30 days to have this assessment done prior to treatment with either allogeneic HCT or additional non-transplant therapies.

8.1.9 Treatment details:

8.1.9.1 Therapy details:

- 8.1.9.1.1 Clinical trial or not.
- 8.1.9.1.2 Name of combination therapy.
- 8.1.9.1.3 Names of each treatment agent.
- 8.1.9.1.4 Details on doses and duration of each therapy agent.

These variables will be assessed at:

- 1) All time-points *after* enrollment.

8.1.9.2 Allogeneic HCT:

- 8.1.9.2.1 Clinical trial or not.
- 8.1.9.2.2 Type of donor graft received: related, unrelated, or cord blood.
- 8.1.9.2.3 Degree of HLA-matching of graft received: matched, single allele mismatch, one antigen mismatch, HLA-haploidentical, or others.

Protocol 2368.00

- 8.1.9.2.4 Type of stem cell source: marrow, peripheral blood, or cord blood.
- 8.1.9.2.5 Type of conditioning regimen: name of agents, doses, and durations.
- 8.1.9.2.6 CMV serology status of patient and donor.
- 8.1.9.2.7 Did acute GVHD develop: date, grade, treatments given for acute GVHD?
- 8.1.9.2.8 Did chronic GVHD develop: date, grade, treatments give for chronic GVHD?
- 8.1.9.2.9 Did the patient relapse after transplant: if yes, date and details on any treatment given for relapse?
- 8.1.9.2.10 If the patient received second transplant: same questions about time of transplant.

These variables will be assessed at:

- 1) After approximately 9, 12, 18, and 24 months after study enrollment or corresponding dates of 3, 6, 12, 18 months after HCT. These dates can be adjusted within a limit of 30 days to have this assessment done prior to treatment with either allogeneic HCT or additional non-transplant therapies.

8.1.10 **AML or MDS response evaluations:**

8.1.10.1 AML or MDs disease status in peripheral blood and/or bone marrow as follows:

- 8.1.10.1.1 Morphology.
- 8.1.10.1.2 Flow cytometry.
- 8.1.10.1.3 Cytogenetics.
- 8.1.10.1.4 Fluorescence in situ hybridization (FISH).
- 8.1.10.1.5 Molecular marker abnormalities.

8.1.10.2 In case of extra-medullary disease:

- 8.1.10.2.1 Flow cytometry of cerebro-spinal fluid.
- 8.1.10.2.2 Physical examination assessment of any soft tissue mass (chloroma).
- 8.1.10.2.3 Imaging descriptions of any soft tissue mass (chloroma).

8.1.10.3 Disease responses:

- 8.1.10.3.1 AML according to the revised recommendations of the International Working Group (IWG) for response criteria and treatment outcomes (please, see study document 'AML Response Criteria').[78]
- 8.1.10.3.2 MDS according to the modified IWG response criteria (please, see study document 'MDS Response Criteria').[79]

These evaluations will be assessed at:

- 1) After approximately 1 month from study enrollment and at least 28 days from last therapy cycle.
- 2) After approximately 3 months from study enrollment and at least 28 days from last therapy cycle.
- 3) After approximately 6 months from study enrollment and at least 28 days from last therapy cycle.
- 4) At 3, 6, 12, and 18 months after day 0 of allogeneic HCT for recipients of HC or at 9, 12, 18, and 24 months from study enrolment for patient not treated with HCT.

Protocol 2368.00

8.1.11 **Toxicity criteria:**

Toxicity will be graded using and adapted version of the CTCAE (NCI Common Terminology Criteria for Adverse Events) Version 4.0 (<http://ctep.cancer.gov>). A copy of the adapted CTCAE v4.0 is available in study document 'Adapted CTC'.

Only toxicities that are graded at III or IV will be documented for this study.

These evaluations will be assessed at:

- 1) After approximately 1 month from study enrollment and at least 28 days from last therapy cycle.
- 2) After approximately 3 months from study enrollment and at least 28 days from last therapy cycle.
- 3) After approximately 6 months from study enrollment and at least 28 days from last therapy cycle.
- 4) At 3 and 18 months after day 0 of allogeneic HCT for recipients of HTC or at 9 and 24 months from study enrollment for patient not treated with HCT.

8.1.12 **Physical Performance:**

The NIH Toolbox 4-Meter Walk Gait Speed Test will be used to measure locomotion. Gait speed is an indicator of the health of physiological systems. Patients will be asked to walk four meters at their usual pace for one practice session and two timed trials. This test takes three minutes to administer. Study coordinators will meet the patients at regularly scheduled medical appointments and will ask them to complete this quick assessment. For patients with no scheduled appointments within the range of administering the 4-meter walk test, study coordinators will mail a self-administered walk test sheet to be completed by the patient. Previous studies have shown that a self-administered, adapted walk test (the Home-Heart-Walk) had a strong intra-class correlation coefficient (0.98) with a standard walk test.[80,81] The test was well received by participants who had a median age of 64 (range: 49 – 80) years old.[81] The study concluded that self-administered walk test is a reliable and useful method of collecting physical activity data in a medically-challenged, older population.[81] We will implement the same restrictions used in that study by excluding patients with documented heart failure, unstable angina pectoris, fever, complex arrhythmia, resting diastolic blood pressure of 100 mm Hg or more or unstable gait from performing the test on their own.[81]

This test will be given at:

- 1) Study enrollment.
- 2) All other time points for collection of patient-reported measures; either performed by study staff at a regularly scheduled medical appointment at study institution or self-administered by patients that do not have a coincidentally scheduled medical appointment.

8.1.13 **Outcomes Data:**

8.1.13.1 Alive or deceased.

8.1.13.2 If deceased: cause(s) of death: Root (underlying cause of death), proximate (immediate cause of death), and contributing causes of death.

Protocol 2368.00

- 8.1.13.3 Disease status: remission, relapse, progression, persistent disease supported with by evidence as in (AML response evaluation).
- 8.1.13.4 For recipients of allogeneic HCT:
 - 8.1.13.4.1 Did acute GVHD develop or not?
 - 8.1.13.4.1.1 If yes: date, grade, organs involved, and treatments given for acute GVHD.
 - 8.1.13.4.2 Current status of acute GVHD: active, resolving, resolved.
 - 8.1.13.4.3 Did chronic GVHD develop or not?
 - 8.1.13.4.3.1 If yes: date, grade, organs involved, and treatments given for chronic GVHD.
 - 8.1.13.5 Current status of chronic GVHD: active, resolving, resolved.
 - 8.1.13.6 Admission to the acute care service within the first 60 days after induction and the first 60 days after consolidation.
 - 8.1.13.7 Admission to the ICU at any time after induction
 - 8.1.13.7.1.1 If yes: dates of admission and discharge from the ICU and hospital, ICU admission diagnosis, most recent AML treatment, and markers of organ failure within 24 hours of ICU admission, including blood counts, blood chemistries, vital signs, and use of life support devices (invasive mechanical ventilation, noninvasive positive pressure ventilation, vasopressors, inotropes, and dialysis). Additionally any positive cultures from 1 week prior to 1 week after ICU admission will be collected.
 - 8.1.13.8 Presence of palliative care referral at any time point after referral to the SCCA.

8.1.14 **Patient-reported QOL measures** (see study document 'Patient Questionnaire Packet):

QOL and symptoms will be assessed longitudinally using 8 measures. All QOL questionnaires will be scored according to the recommendations of the developers. We estimate it will take 15 minutes to complete the questionnaires. Please, see study document 'Patient Questionnaire Packet' for the measures of patient-reported QOL.

The Functional Assessment of Cancer Therapy Bone Marrow Transplant (FACT-BMT, version 4) Scale is a 49-item patient-reported outcome questionnaire that measures QOL in bone marrow transplant patients. The questionnaire includes the standard form of the FACT instrument, namely the FACT-G and a separate BMT scale consisting of 12 items. The BMT scale was enlarged during the validation procedure from 12 to 22 items by McQuellon et al. [82] The FACT-BMT measures physical, functional, social/family and emotional well-being and BMT-specific concerns. All items are rated on a five-point Likert scale. The FACT instrument was recommended by Andrykowski for the investigation of QOL in BMT patients. [83] Patients will be asked to comment on the statements with regard to the time period of the week immediately preceding the specific study time point. To lessen the burden on patients, we will only use the parameters under the standard form of FACT.

The EQ-5D [84] will be used to capture participant-reported utilities that may be used to calculate quality adjusted survival. The EQ-5D contains a five-item survey with three response levels per item measuring mobility, self-care, usual activities, pain/discomfort and anxiety/depression. Conversion tables allow scoring from the 5 items into a summary utility score.

Protocol 2368.00

The Social Activity Log (SAL) was designed to capture the frequency and diversity of social activities outside of daily responsibilities. The SAL was adapted by Syrjala et al [85] from one of the few existing measures of social activity participation, the Pleasant Events Schedule. [86] The SAL was developed to focus on activities of survivors with people other than those with whom the survivors live. This was done by reviewing the original content of the Pleasant Events Schedule and identifying items that represented social activities of adults. This content was then reviewed by a focus group of 8 non-cancer adult volunteers who considered their own activities of the previous month and added or revised items. The resulting items were then completed by two sets of volunteers. In that study, the SAL possessed good internal consistency (Cronbach's $\alpha = 0.82$). Internal consistency for non-contact was $\alpha = 0.81$, regular events $\alpha = 0.75$ and special events $\alpha = 0.63$. SF-36 social function and SAL were moderately correlated ($r = .31$) as an evidence of convergent validity.

To further measure social support, we will use the ENRICH Social Support Instrument (ESSI) [87,88]. This scale was created from items from other validated measures of social support; these items were chosen for their documented predictive validity. Unlike the SAL which measure objective participation in social activities, this measure taps patients' perception of social support, both physical and emotional. The response categories for the seven items range from 1 (none of the time) to 5 (all of the time). Created for use with patients with cardiac disease, it was found to be predictive of death and to have good internal consistency (Cronbach's $\alpha = 0.86$) [79]. The social support measure has also been used in the transplant population but results are not published yet (Syrjala K, Personal Communications).

Depression is a common psychiatric condition during cancer treatment. Most prevalence estimates have ranged between 10 and 25%. [89] Depression could increase symptom burden, [90] affects cognition, [91] QOL, [92] and survival. [74,93,94] We selected the Patient Health Questionnaire-9 (PHQ-9) depression scale as our measure for depression. [95] The PHQ-9 parallels the nine diagnostic symptom criteria of the DSM-IV for Major Depressive Disorder (MDD). The format and temporal framework of the items also correspond to the DSM-IV criteria and can facilitate the follow-up review of symptoms and diagnostic process. With 9-items, participants will rate the frequency of the 9 symptoms over the past 2 weeks on a 4-point Likert scale (0 = not at all, 1 = several days, 2 = more than half of the days, and 3 = nearly every day). [83] The total score of the PHQ-9 ranged from 0 to 27, with higher scores indicating greater severity of depressive symptoms. The internal reliability was reported to be high (Cronbach $\alpha = .91$). Major depressive disorder is diagnosed if 5 or more of the 9 depression symptoms have been present at least "more than half the days" in the past 2 weeks and if one of the symptoms is depressed mood or anhedonia. One of the 9-symptom criteria ("thoughts that you would be better off dead or of hurting yourself in some way") counts as one of the diagnostic criteria for depressive disorders if present at all, regardless of duration. [96] According to the recommendation of Kroenke et al, [96] scores of 0 to 4, 5 to 9, 10 to 14, 15 to 19, and 20 or greater are used to define 5 groups with increasing severity of depressive symptoms. At only 9 items, the PHQ-9 is shorter than most depression screening measures. Unlike most other measures of depression, the PHQ-9 was developed, tested and refined for use with medical patients. This is important because the criterion validity was established in a population with high rates of other physical symptoms and associated non-specific psychological distress. It has also demonstrated acceptability among non-psychiatric patients and among busy primary care providers. [95-97] It is sensitive to change and treatment effects, [98] making it a valid longitudinal clinical tool.

Physical activity as a component of the Fried Frailty Index is measured by a subscale of the Medical Outcomes Study (MOS) Physical Health. The MOS Physical Health Scale measures a broad range of physical functioning, with questions ranging from “Can you bathe and dress yourself?” to “Can you perform vigorous activities, such as running or lifting heavy objects?” Items are rated on a 3-point Likert scale measuring independence in performing the activity. Internal consistency of the physical function score is 0.92.[99]

QOL measures will be assessed at:

- 1) Study enrollment.
- 2) After approximately 1 months from study enrollment and at least 28 days from last therapy cycle.
- 3) After approximately 3 months from study enrollment and at least 28 days from last therapy cycle.
- 4) After approximately 6 months from study enrollment and, if necessary, adjusted within a limit of 30 days to have this assessment done prior to treatment with either allogeneic HCT or additional non-transplant therapies.
- 5) At 3, 6, 12, and 18 months after day 0 of allogeneic HCT for recipients of HTC or at 9, 12, 18, and 24 months from study enrollment for patient not treated with HCT.

8.1.15 OARS Multidimensional Functional Assessment Questionnaire (OMFAQ):

Each patient will complete an assessment of his/her respective functional status as a measurement of ability to perform activities of daily living. A portion of the OARS Multidimensional functional Assessment Questionnaire (OMFAQ) will be administered, as it gives a view of the patient’s functional status and independence, including: social, economic, mental and physical health, and self-care capacity. The first part includes seven questions regarding the instrumental activities of daily living (commuting, cooking, shopping, and ability to handle finances). The second part includes seven questions regarding the activities of daily living (bathing, dressing, toileting, walking). The scores range from 0 to 2, with lower scores indicating higher levels of dependency on others to complete the activities. The assessment is estimated to take 5 minutes. The OMFAQ will be scored according to the recommendations of the developers. The measures have good validity [100].

These variables will be assessed at:

- 1) Study enrollment.
- 2) After approximately 1 months from study enrollment and at least 28 days from last therapy cycle.
- 3) After approximately 3 months from study enrollment and at least 28 days from last therapy cycle.
